## 5.2.2 Primary efficacy analysis

### 5.2.2.1 Primary analysis of the primary endpoint

The primary efficacy endpoint is a binary variable (Responder / Non-responder) based on the change from baseline to Week 24 of the A Score (see section 4.5.4.1.6).

The primary population of analysis will be the FAS as described in section 4.3.3. The primary imputation method described in section 4.1.6.3 will be used for missing data replacement.

#### **Descriptive analysis**

The number (% with its 95% confidence interval) of responders and non-responders at Week 24 will be summarized in a table using descriptive statistics by treatment group and diabetic status.

The reason for non-response (No decrease of 2 points of SAF-A score, Worsening of CRN-F score, Both, No post-treatment biopsy available) will also be displayed.

#### **Evaluation of treatment effect (each dose versus placebo)**

Each treatment dose will be compared to placebo using a CMH test stratified on the diabetic status.

In order to take into account multiplicity of tests, the ascending Hochberg procedure will be applied (see section 4.1.5 for details). The p-values of the 2 tests will be provided and will provide conclusions regarding the primary objective of the study met or not met.

Corresponding CMH Odds ratio (OR) and adjusted-Relative Risk (RR) will be provided with their 95% confidence intervals, in the FAS for the two lanifibranor groups.

The Breslow-Day test will be implemented for homogeneity of the odds ratios between diabetic and non-diabetic patients:

- If the test is significant, then this means that the treatment effect has not the same magnitude in diabetic and non-diabetic patients (significant difference in OR in the 2 populations)
- If the test is not significant, then this means that the treatment effect has the same magnitude in diabetic and non-diabetic patients (no significant difference in OR in the 2 populations).
- Regardless the significance of the test, both OR and RR in diabetic and non-diabetic patients will be provided with their 95% confidence interval

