#### 9.7.4 *Efficacy Analyses*

##### Primary efficacy analysis

The primary population will be the intent to treat FAS population composed of all randomized subject who received at least one dose.

The primary efficacy endpoint will be a binary variable (responder / non responder) based on the change from baseline to Week 24 of the SAF activity score. Responder is defined as a decrease from baseline to week 24 of at least 2 points of the SAF activity score combining hepatocellular inflammatory and ballooning without worsening of fibrosis.

The primary tests of hypotheses will be the Cochran Mantel Haenszel test stratified on diabetes comparing the high dose to placebo and the low dose to placebo. The ascending Hochberg procedure will be used for adjusting the type one error which is globally set at 0.05 two-sided. The primary measure of the effect size will be the CMH odds ratio with an adjustment for diabetes. Because the odds ratio is not easy to interpret when the rate of responders in the placebo group is not very small the odds ratio (OR) and its confidence interval will be converted in Risk Ratio (RR) using the following formula  $RR = (P_1/P_0) = OR / [(1-P_0) + (P_0 \times OR)]$  (75). The log-binomial model will preferentially be used in the absence of convergence or estimability issue for estimating the effect size with RR.

The primary rule for handling the missing data is to consider non-responders all patients who are not confirmed responders.

The primary handling of centers is to ignore in the primary analysis the center effect because 30+ centers should be involved in the study and the number of empty cells in the breakdown of the site by treatment by stratum table can be large (sparse contingency table).

The primary handling of multiplicity of testing will be done through the Hochberg procedure.

The primary handling of heterogeneity of result across strata will be performed through the Breslow-Day test. If the homogeneity hypothesis is rejected, then the estimate of the difference in percentage points between each dose and placebo along with the 95% C.I. will be calculated within each stratum. If the interaction between stratum and treatment (Breslow Day test) is significant it means that the treatment effect has not the same magnitude in diabetic and non-diabetic patients. In the absence of qualitative interaction there will be no further adjustment of the type one error for multiplicity of testing.

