## 4.2 Sample size calculation

The expected rate of responders according to the retained definition was estimated to 10% for the placebo by a group of clinical experts. An excess rate of responders of 20% was accepted as clinically pertinent. It corresponds to a multiplication of chance of success (responders) of 3 and a NNT (Number Needed to Treat) of 5. The sample size required to reach a power of at least 80% is 72 patients per group with a two-sided alpha of 0.025 (adjustment for multiplicity). The sample size is sensitive to the rate of responders in the placebo group. For example, if the rate of responders is 15% instead of 10% then 85 patients are required. If the true rate is lower than 10% then less patients may be sufficient. The sample size is therefore rounded in the conservative side of 75 patients per group.

Based on the experience of previous clinical trials, it is estimated that 100 patients per group will need to be screened to randomise 75 patients after central reading of liver biopsy confirms the NASH diagnosis and activity (screening failure rate of 25%). However, as detailed in section 3.5, the observed screening failure rate was of 72%), consistent with all other clinical trial performed in NASH with such a high screening failure rate.

In case the end of study liver biopsy slides are not available or not interpretable in more than 5% of patients, an amendment will be submitted to increase sample size accordingly.

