### 4.7 Analysis of sub-groups/complementary analysis

Subgroup analysis described thereafter, will not be performed if there are not enough patients (i.e. less than 15% in one category).

Main subgroups of interest are:

- Diabetic status at baseline (Yes, No)
- Biopsy length at baseline ( $\leq 8$ ,  $>8$  mm)
- NAS score at baseline ( $< 6$ ,  $\geq 6$ )
- SAF-A score at baseline (A2-A3, A4)
- CRN-F score at baseline (F0-F1, F2-F3)
- BMI at baseline (Obese, Non-obese)
- Metabolic syndrome at baseline (Yes, No)
- Insulin-resistance status at baseline (Yes, No)
- By site group No. 1 (Bulgaria, all other countries)
- By site group No. 2 (3 or less patients randomised and treated, from 4 to 9 patients randomised and treated, 10 or more patients randomised and treated)
- Sex (Male, Female)

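### The primary CMH test adjusts for diabetes only; also stratifying on baseline SAF activity (A2-A3 v A4) is a cheap improvement that gains power if that score is materially prognostic

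*SAP*

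**What the plan says.** - **Primary test.** SAP 5.2.2.1: "Each treatment dose will be compared to placebo using a CMH test stratified on the diabetic status". Protocol 9.7.4 specifies the same test, and protocol 9.3 makes diabetes the only randomisation stratum.
- **Multiplicity.** Protocol 9.7.4: "The ascending Hochberg procedure will be used for adjusting the type one error which is globally set at 0.05 two-sided".
- **Endpoint.** Response is a fall of at least 2 points in SAF-A without fibrosis worsening (SAP 4.5.4.1.6). Entry requires SAF-A of 3 or 4 on central reading (protocol 4.2.1).
- **Baseline SAF-A.** It is tabulated as A2, A3 and A4 (SAP 5.1.7). It is listed as a subgroup, "SAF-A score at baseline (A2-A3, A4" (SAP 4.7), and that subgroup analysis is descriptive only (SAP 5.2.2.3).
- **Other analyses of the primary endpoint.** The sensitivity table in SAP 5.2.2.2 varies the population and the handling of missing data, not the covariates. SAP 5.2.2.4 adds dose-response, dose comparison, site grouping and a model with weight change. None adjusts for baseline SAF-A.
- **Sample size.** SAP 4.2 starts from the control arm: "The expected rate of responders according to the retained definition was estimated to 10% for the placebo". On the effect to be detected it says: "An excess rate of responders of 20% was accepted as clinically pertinent". The resulting size is: "The sample size required to reach a power of at least 80% is 72 patients per group". The test level behind that figure is given as "with a two-sided alpha of 0.025 (adjustment for multiplicity".

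**The concern.** The endpoint is a change on the SAF-A scale, so the starting score may well bear on who responds. An A4 patient must reach A2 or lower, and an A3 patient A1 or lower. If baseline SAF-A predicts response, leaving it out has two consequences.

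- Some precision already paid for by the screening biopsy is not used.
- A chance difference between arms in the A4 share passes straight into the primary comparison, because neither the randomisation nor the test deals with it.

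The plan has no inferential analysis that would show whether such a difference drove the result. SAP 4.7 drops a subgroup analysis when a category holds less than 15% of patients, so even the descriptive table could be lost if few patients are A4.

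**Working it through.** **1. The plan's own sample size.** With unpooled variance,

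n = (z_0.9875 + z_0.80)² × [p0(1-p0) + p1(1-p1)] / 0.20², where (2.2414 + 0.8416)² = 9.505.

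- 10% v 30%: 9.505 × (0.09 + 0.21) / 0.04 = 71.29, so 72.
- 15% v 35%: 9.505 × (0.1275 + 0.2275) / 0.04 = 84.36, so 85. This agrees with "if the rate of responders is 15% instead of 10% then 85 patients are required".

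Both stated figures reproduce. At the planned 75 per arm, power by the pooled-variance formula is 80.2%.

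**2. Effect of adding the stratum.** Each simulated trial was analysed twice without continuity correction: by CMH on diabetes (2 strata) and by CMH on diabetes × SAF-A (4 strata).

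- From the documents: 10% v 30% overall, 75 per arm, two-sided 0.025.
- Assumed, because the documents are silent: 50% A4, 40% diabetic, diabetes not prognostic and independent of SAF-A, and a common treatment odds ratio (OR).
- 200,000 trials per row.

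| Prognostic OR, A4 v A2-A3 | Diabetes only | Diabetes × SAF-A | Change (points) |
|---|---|---|---|
| 1.0 | 81.3% | 80.7% | -0.6 |
| 1.5 | 81.5% | 81.1% | -0.4 |
| 2 | 81.3% | 81.4% | +0.1 |
| 3 | 81.5% | 82.6% | +1.1 |
| 5 | 81.5% | 84.4% | +2.8 |

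The inverse direction behaves alike: -0.3 at OR 0.67, +0.1 at 0.5 and +1.2 at 0.33.

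**3. Sensitivity to the assumptions.**

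- Only 10% A4: about -0.5 at OR 2, 0 at OR 3 and +1.5 at OR 5, so break-even moves to about 3.
- Constant 20-point effect in both groups: -0.3 at OR 2 and 0.0 at OR 3.
- Effect larger in A2-A3 (30 v 10 points): -0.4 to -0.6 for OR 1.5 to 3.
- Effect larger in A4 (10 v 30 points): +0.5 to +2.0 over the same range.
- At the 247 actually randomised (SAP 3.5; 247 / 3 ≈ 82 per arm) the pattern is the same: about -0.2 at OR 1.5, +1 at OR 3 and +2.5 at OR 5.

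**4. Type I error.** With no drug effect, the upper-tail rejection rate was about 0.011 for the planned test and 0.012 for the four-stratum test, against a nominal 0.0125.

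**5. Chance imbalance.** With 82 per arm and 50% A4, two arms differ by 10 points or more in A4 share in about 18% of trials. Conditional on such an imbalance:

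- Drug arm short of A4 patients, 10% v 30% overall: power is about 76 to 77% with the planned test and 86% with the stratified test at OR 3, and about 79% and 85% at OR 2.
- Drug arm with excess A4 patients, no drug effect, 20% response in both arms: upper-tail error at OR 3 is 2.8% with the planned test and about 1.2 to 1.3% with the stratified test, against a nominal 1.25%. At a 10% response rate the figures are about 2.1% and 1.2%.

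**The case against.** The case for leaving the plan alone is substantial.

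- **The test matches the randomisation and the protocol.** Diabetes is the randomisation stratum and the pre-specified stratifier. The test is valid without baseline SAF-A, and planned power is reached. This stands.
- **The premise is not documented.** Nothing states the A4 share or its association with response. Both groups need the same 2-point fall, and eligibility restricts the score to 3 or 4. This stands, and it is why the size can only be given as a range.
- **Imbalance will be visible.** Baseline SAF-A is tabulated by arm, and response is reported by SAF-A subgroup with confidence intervals. True, but neither gives an adjusted comparison of each dose with placebo.
- **Changing the primary test late is awkward.** The SAP is dated July 2020, after all patients were randomised. The Breslow-Day step is written for diabetic v non-diabetic patients, and the adjusted odds ratio and its conversion to a risk ratio would change. This is a fair reason to prefer the sensitivity analysis.
- **Sparse strata.** The protocol leaves centre out for this reason. Four strata are a milder case: 75 × 0.4 × 0.5 = 15 per arm in the smallest stratum with half A4, but 75 × 0.4 × 0.1 = 3 with 10% A4.

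A reader might also infer that adding any prognostic baseline value must raise power. The calculation does not support that: a weakly prognostic stratum costs a little, and a larger effect in A2-A3 can turn the change negative even at OR 3.

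**Conclusion.** The omission is real, but it is an efficiency and robustness point, not a defect. It would be wrong to read it as bias or inflated type I error: averaged over randomisations both tests hold their level, and the conditional figures above describe only trials with an unlucky imbalance.

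For prognostic odds ratios from 1 to 5, the expected change in power runs from about -0.6 to +3 points, with break-even near 2. This rests on half the patients being A4, 40% being diabetic and a common treatment odds ratio. Break-even is higher if few patients are A4 or if the effect is larger in A2-A3. The downside is limited to about half a point in the cases examined. In return the comparison is protected against chance imbalance in baseline activity, using a variable the SAP already derives. It is a cheap improvement.

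**What to change.** Before unblinding, do one of the following.

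1. In SAP 5.2.2.1, stratify the CMH by diabetes × baseline SAF-A (A2-A3, A4). Leave Hochberg unchanged, keep the Breslow-Day test for diabetes as written, and state that the odds ratio and risk ratio are adjusted for both factors. Record the departure from the protocol in SAP 4.6.4.
2. If the protocol test stays primary, add a row to the table in SAP 5.2.2.2: FAS, primary imputation, CMH stratified by diabetes × baseline SAF-A (A2-A3, A4). That section still carries an unresolved drafting note, so it needs editing anyway.

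Use the SAP grouping A2-A3 v A4 rather than A3 v A4, because the SAP allows for baseline A2 readings.

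Cost: minor SAP rewording and no new data. Option 1 risks about half a point of power if baseline SAF-A is weakly prognostic or not prognostic; option 2 costs the primary test nothing.

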#### *4.1.5 Treatment groups comparison*

For statistical tests, the type I error risk of these will be set at 5% (2-sided) without adjustments for multiplicity testing, unless specified otherwise.

P-values will be presented with 3 decimals. Any p-value less than 0.001 will be presented as <0.001, even if it would normally round up to 0.001.

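### SAP 5.2.2.1 reads a non-significant Breslow-Day test as equal effect in diabetic and non-diabetic patients, although the test has little power to detect even a large difference

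*SAP*

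**What the plan says.** SAP 5.2.2.1, under the evaluation of each dose against placebo, applies the Breslow-Day test to the ORs in diabetic and non-diabetic patients and gives three bullets.

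- A significant result is read as an effect of different magnitude in the two groups.
- For the opposite result: "If the test is not significant, then this means that the treatment effect has the same magnitude in diabetic and non-diabetic patients". A closing parenthesis adds that the ORs did not differ significantly.
- "Regardless the significance of the test, both OR and RR in diabetic and non-diabetic patients will be provided with their 95% confidence interval".

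SAP 4.1.5 and protocol 9.7.4 describe the same test but interpret only a significant result. Both promise within-stratum differences in percentage points only if homogeneity is rejected. Neither document gives a power for the test, an equivalence margin, an interaction size of interest or an expected diabetic share. Protocol 9.3 says the strata are filled without a quota.

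No separate level is set for this test, so the general rule in SAP 4.1.5 applies: "the type I error risk of these will be set at 5% (2-sided) without adjustments for multiplicity testing, unless specified otherwise".

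**The concern.** A non-significant test of homogeneity shows only that the data did not contradict equal ORs at the chosen level. It supports near-equality only if the test would probably have detected a difference that matters, or if the interval for the difference is narrow. The SAP requires neither.

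Diabetes is the only randomisation stratum, so consistency across it is the obvious first question after the primary result. A report that follows the bullet could describe the effect as equal in the two groups when the data are compatible with benefit in only one of them.

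The method of 5.2.2.1 is also reused for the sensitivity analyses (5.2.2.2), for 1200 mg against 800 mg (5.2.2.4) and for the binary histology endpoints (5.2.3.1 to 5.2.3.7 and 5.2.3.14). The same reading would carry over to those analyses, most of which also stratify on diabetes. Protocol 9.7.4 lets SAP clarifications of the analysis prevail over other interpretations of the protocol, so the protocol's silence on non-significant results does not correct the bullet.

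**Working it through.** **1. The plan's own sample size.** SAP 4.2 takes the placebo rate as "estimated to 10% for the placebo by a group of clinical experts" and states: "An excess rate of responders of 20% was accepted as clinically pertinent". That is 10% against 30%, at two-sided alpha 0.025. With unpooled variance,

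n = (z₀.₉₈₇₅ + z₀.₈₀)² × [p₀(1−p₀) + p₁(1−p₁)] / (p₁−p₀)²

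- 10% v 30%: (2.241 + 0.842)² × (0.09 + 0.21) / 0.04 = 71.3, so 72. The SAP agrees: "The sample size required to reach a power of at least 80% is 72 patients per group".
- 15% v 35%: (2.241 + 0.842)² × (0.1275 + 0.2275) / 0.04 = 84.4, so 85. The SAP agrees: "if the rate of responders is 15% instead of 10% then 85 patients are required".

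The planning figures reproduce. They concern the main comparison, not the homogeneity test.

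**2. Inputs for the homogeneity test.**

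- Patients per arm: 75 planned (SAP 4.2). 247 were randomised 1:1:1 (SAP 3.5 and 3.2), and 247/3 is about 82. Missing outcomes count as non-response (SAP 4.1.6.3), so n is not reduced.
- Planning OR: (0.30/0.70) / (0.10/0.90) = 3.86.
- Level: two-sided 5% (SAP 4.1.5).
- Assumed, because the documents do not say: diabetic share 30–60%, and the same placebo rate in both strata.

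**3. One case by hand (Wald approximation).** Take 82 per arm, 40% diabetic, placebo 10% in both strata, and ORs a factor of two apart around 3.86: 5.455 in diabetic and 2.727 in non-diabetic patients. The active rates are then 37.7% and 23.3%. The variance of the difference in log OR is the sum of 1/[n p(1−p)] over the four cells, with 32.8 diabetic and 49.2 non-diabetic patients per arm:

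0.130 + 0.339 + 0.114 + 0.226 = 0.808, so SE = 0.899.

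ln 2 / 0.899 = 0.771. Power = Φ(0.771 − 1.96) + Φ(−0.771 − 1.96) = 0.117 + 0.003 = 12%.

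The 95% CI for the ratio of the two ORs would run from its lower to its upper limit over a factor of exp(2 × 1.96 × 0.899), about 34.

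The same calculation with OR 4 in diabetic and 1 in non-diabetic patients gives SE 0.966 and ln 4 / 0.966 = 1.435, so power is about 30%.

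**4. The Breslow-Day test itself.** The statistic is the sum over strata of (a − E)²/V. Here a is the number of responders on the dose, and E and V are its expected value and variance under the common Mantel-Haenszel OR. It is referred to chi-square on 1 df. Simulation used 40,000 trials per scenario, 75 or 82 per arm and diabetic share 30–60%. The simulated type I error was 5.2–5.3%.

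| Placebo v active rate | True difference | Power |
|---|---|---|
| 10% v 30% (planning) | ORs differ two-fold | about 10–13% |
| 15% v 35% | ORs differ two-fold | about 12–15% |
| 20% v 40% | ORs differ two-fold | about 14–17% |
| 30% v 50% | ORs differ two-fold | about 15–19% |
| placebo 10% | OR 4 v OR 1 | about 26–32% |

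The last row means a miss in 68–74% of trials. At the planning rates, 80% power would need ORs that differ by a factor of about 15–20 (Wald approximation, diabetic share 30–50%).

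**The case against.** The strongest reply is that little depends on the sentence. The CMH tests, the Hochberg adjustment and the conclusion on the primary objective are all set without reference to it. The next bullet reports stratum ORs and RRs with 95% CIs in every case, and the descriptive analysis gives responder rates with CIs by treatment and diabetic status. A reader will therefore see how wide the stratum intervals are. The closing parenthesis can be taken to limit the bullet to the test result, and the wording appears nowhere else in the plan. All of this stands as a limit on the harm.

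It does not make the bullet right. The parenthesis gives the basis for the inference, while the main clause still draws the conclusion of equal magnitude. Reporting the intervals supplies the right data but leaves the wrong instruction for reading them, and no interval is planned for the contrast that the test addresses.

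Three stronger readings might be inferred, and the documents do not support them. The SAP does not claim that equality is proved. Nothing here suggests that the effect really does differ by diabetic status. And no single power figure can be quoted without conditions, because the diabetic share is not documented and the answer moves with the placebo rate.

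**Conclusion.** The point holds as an error of stated interpretation. A non-significant Breslow-Day test in this trial says very little about equality: power is about 10–13% for a two-fold ratio of ORs at the planning placebo rate of 10%, and no more than about 19% if the placebo rate is 30%. Even no benefit in one stratum against an OR of 4 in the other would usually go undetected at the planning rate.

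These figures assume a diabetic share of 30–60%, equal placebo rates in the two strata, 75–82 patients per arm and a single dose compared with placebo. The qualitative conclusion does not depend on where in those ranges the trial falls.

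The primary result stays as planned. What is at risk is the statement about consistency across the only stratification factor, for the primary endpoint and for the endpoints that borrow its method.

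**What to change.** Replace the second bullet in SAP 5.2.2.1 with: *A non-significant result means no evidence of heterogeneity was found; it does not show that the effects are equal. Interpret the stratum ORs and their 95% CIs.*

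Beside the Breslow-Day p-value, report the ratio of the two stratum ORs with its 95% CI. It can be derived from the stratum ORs and intervals already planned, but showing it directly saves the reader from comparing two wide intervals by eye.

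The cost is one SAP sentence and one extra table line. The endpoints that refer back to 5.2.2.1 pick up the change without further edits. No new data or additional test is needed.

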### 5.2.2.2 Sensitivity analyses

Several sensitivity analyses will be performed on the primary criterion as detailed in table below. Each time, descriptive analysis and evaluation of treatment effect (each dose versus placebo) will be performed as detailed in section 5.2.2.1.

To be confirmed. Indeed qualitative endpoint and not quantitative one => CMH and not MMRM ....

Analysis population	Treatment group	Missing data replacement
FAS	Actual treatment received	Observed cases under treatment*
Randomized set	Randomized treatment assigned	Primary imputation method
PP	Actual treatment received	Observed cases under treatment
EPP	Actual treatment received	Secondary imputation method
FAS	Actual treatment received	Observed cases

\* This analysis corresponds to analyses on completers (biopsy at week 24 performed, within maximum 14 days after last intake).

